- Fasting blood for serum bone biomarkers at Baseline, and at Weeks 4, 12, 24, 48, 72, 96/ED
- Fasting urine for renal biomarkers at Baseline, and at Weeks 4, 12, 24, 48, 72, and 96/ED for all subjects except Part A, cohort 2 (ESRD subjects on HD)

- Hip and Spine DXA Scans will be conducted at Weeks 24, 48, 72, and 96/ED. The ED visit DXA should be done if not done within the last 12 weeks of this visit.
- ECG will be performed at Weeks 48 and 96/ED
- CCI 
- Sequence analysis of the HBV polymerase/reverse transcriptase (pol/RT) for resistance surveillance may be performed at Baseline for subjects with HBV DNA ≥ 69 IU/mL and may be attempted for viremic subjects (HBV DNA ≥ 69 IU/mL) at Weeks 24, 48, and 96/ED. Phenotypic analysis will be performed for subjects that are subjected to sequence analysis. As it may not be known at the time of the visit whether a subject is viremic or if it will be their last study visit, a separate virology sample for potential resistance surveillance will be collected at each study visit.
- In the event of unconfirmed virologic rebound (HBV DNA ≥ 20 IU/mL), subjects will be asked to return to the clinic for a scheduled or unscheduled blood draw.
 - For virologic rebound occurring within the first 12 weeks of the study, the next scheduled visit will be used for follow up.
 - For virologic rebound occurring after Week 12, the subject will return for an unscheduled visit 2-3 weeks after the date of the original test that resulted with HBV DNA virologic rebound for confirmation of virologic rebound. At this follow up visit, a serum blood sample for resistance testing will be obtained. For unscheduled visits, the subject will be required to bring their supply of study drug with them and be assessed for adherence by pill count, and if necessary, the subject will be re-counseled on adherence to study medication.
- Plasma, serum, and urine will be collected at Baseline and at every on-treatment visit thereafter for storage for all subjects. Urine for storage will be collected where available for subjects in Part A, Cohort 2 (ESRD subjects on HD).

- Health Related Quality of Life (HRQoL) Surveys (SF-36, CLDQ, WPAI, and EQ-5D-3L) at Baseline, Weeks 24, 48, and 96/ED. The ED visit HRQoLs should be done if not done within the last 24 weeks of this visit.
- Health Utilization Questionnaire will be administered by site staff at Baseline and at every on-treatment visit thereafter.

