6.5. Early Discontinuation (ED)/Unscheduled Visit

A subject should attend an unscheduled visit if requested by the sponsor or the investigator.

The assessments at the unscheduled visits are at the investigator's discretion. At all unscheduled visits initiated for the purpose of confirming virologic rebound a serum blood sample for resistance testing must be collected.

If a subject discontinues study dosing (for example, as a result of an AE), every attempt should be made to keep the subject in the study and continue to perform the required study-related follow-up and procedures (see Section 6.6, Criteria for Discontinuation of Study Treatment). If this is not possible or acceptable to the subject or investigator, the subject may be withdrawn from the study.

The ED Visit should be performed within 72 hours (i.e., visit window is + 3 days) of the last study drug dose.

- Complete physical exam with vital signs (blood pressure, pulse, respiration rate and temperature) and body weight
- ECG (subjects must rest quietly in the supine position for a minimum of 5 minutes prior to the recording)
- DXA scan of spine and hip to be performed within \pm 14 days of the expected visit date and is done only if not done within the past 12 weeks of the ED visit
- Review concomitant medications
- Review adverse events
- Fasting blood sample for serum bone biomarkers and metabolic assessment (glucose and lipid panel [total cholesterol, HDL, direct LDL, and triglycerides]) – no food or drinks, except water, at least 8 hours prior to blood collection (only collected if not done in the last 12 weeks)
- Fasting urine sample for renal biomarkers for all subjects except for Part A, Cohort 2 (ESRD subjects on HD) – no food or drinks, except water, at least 8 hours prior to blood collection(only collected if not done in the last 12 weeks)

- Blood sample for serum chemistry and liver function tests (including PT/INR), hematology, plasma HBV DNA level, serum HBsAg (quantitative), HBV serology (qualitative HBsAg and HBeAg), eGFR_{CG}, virology (resistance surveillance), sparse plasma PK (all subjects except Part A, Cohort 2 [ESRD subjects on HD]), and serum and plasma for storage
- Blood sample for Fibrotest[®]
- CPT ([Appendix 7] Assessment requires: total bilirubin, albumin, PT/INR, Ascites assessment, and Hepatic encephalopathy assessment) for Part B subjects (hepatic impairment) only

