- MELD Score (Assessment requires: total bilirubin, serum creatinine, serum sodium, and PT/INR) for Part B subjects (hepatic impairment) only
- Urine sample (for all subjects except only where available for subjects in Part A, Cohort 2 [ESRD subjects on HD]) for urinalysis, pregnancy test (for females of child-bearing potential; in case of a positive urine test, or if urine cannot be collected for subjects in Part A, Cohort 2 [ESRD subjects on HD], a serum pregnancy test will be done), and for storage.
- Health Related Quality of Life (HRQoL) Surveys (CLDQ, SF-36, WPAI, EQ-5D-3L) are done only if not done within the past 24 weeks of the ED visit
- Site-administered questions for Health Utilization Assessment to be completed

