Appendix 2. Study Procedures Table

[figure not shown]

Study Procedures	Visit Windows ^k		± 3 Days			± 14 Days						ED ^l	Follow Up ^m
	Screening (45 days)	Baseline (Day 1)	Week 4	Week 8	Week 12	Week 24 ^k	Week 36	Week 48 ^k	Week 60	Week 72	Week 96 ^k		
Informed Consent	x												
Inclusion/Exclusion Criteria	x	x											
Medical History (including HBV disease and treatment history)	x	x											
Concomitant Medications	x	x	x	x	x	x	x	x	x	x	x	x	x
Adverse Events	x	x	x	x	x	x	x	x	x	x	x	x	x
Complete Physical Examination with weight and vital signs ^a	x	x				x		x		x	x	x	
Height	x												
Body Weight	x	x	x	x	x	x	x	x	x	x	x	x	x
Vital Signs ^a	x	x	x	x	x	x	x	x	x	x	x	x	x
Symptom driven Physical Examination			x	x	x		x		x				x
Health Related Quality of Life (CLDQ, SF-36, WPAI, EQ-5D-3L) ^b		x				x		x			x	x	
Health Utilization Assessment		x	x	x	x	x	x	x	x	x	x	x	
Serum Chemistry, Hematology, and Liver Function Tests ^c	x	x	x	x	x	x	x	x	x	x	x	x	x
Fasting Metabolic Assessment ^d		x				x		x		x	x	x	
Pregnancy testing (women of child-bearing potential only)	serum	urine (+ve test to be confirmed with serum; serum test will also be collected if urine cannot be collected for subjects in Part A, Cohort 2 [ESRD subjects on HD])											
	x	x	x	x	x	x	x	x	x	x	x	x	x
Estimated Glomerular Filtration Rate by Cockcroft-Gault method (eGFR _{CG})	x	x	x	x	x	x	x	x	x	x	x	x	x

Study Procedures	Visit Windows ^k		± 3 Days			± 14 Days						ED ^l	Follow Up ^m
	Screening (45 days)	Baseline (Day 1)	Week 4	Week 8	Week 12	Week 24 ^k	Week 36	Week 48 ^k	Week 60	Week 72	Week 96 ^k		
HBV serology (qualitative HBsAg and HBeAg) and quantitative HBsAg ^e	x	x			x	x	x	x	x	x	x	x	x
HCV, HDV, HIV Testing	x												
α-fetoprotein (AFP) ^f	x												
Urinalysis ^g	x	x	x	x	x	x	x	x	x	x	x	x	x
Urine drug screen ^g	x												
DXA scans (Hip & Spine) ^h	x					x		x		x	x	x	
ECG ⁱ	x							x			x	x	
Plasma HBV DNA level	x	x	x	x	x	x	x	x	x	x	x	x	x
FibroTest [®]		x				x		x			x	x	
CPT and MELD Scores (Part B subjects [hepatic impairment] only) ^j	x	x				x		x			x	x	
Serum Cystatin C ⁿ		x											
Fasting Blood for Bone Biomarkers, Fasting Urine for Renal Biomarkers ^o		x	x		x	x		x		x	x	x	
Fracture Risk Assessment (FRAX)		x											
Virology (Sequence analysis of HBV pol/RT for resistance surveillance) ^p		x	x	x	x	x	x	x	x	x	x	x	
Vitamin D		x				x		x					
Sparse Plasma PK (All subjects except Part A, Cohort 2 [ESRD subjects on HD]) ^q		x	x	x	x	x	x	x	x	x	x	x	

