Sparse Plasma PK (Part A, Cohort 2 [ESRD subjects on HD]) ^r			x	x	x	x							

[figure not shown]
CCI

Study Procedures	Visit Windows ^k		± 3 Days			± 14 Days						ED ^l	Follow Up ^m	
	Screening (45 days)	Baseline (Day 1)	Week 4	Week 8	Week 12	Week 24 ^k	Week 36	Week 48 ^k	Week 60	Week 72	Week 96 ^k			
CCI														
Serum, plasma, and urine ^g for storage		x	x	x	x	x	x	x	x	x	x	x	x	x (serum only)
Study Drug Accountability			x	x	x	x	x	x	x	x	x			
Study Drug Dispensation		x	x	x	x	x	x	x	x	x				
In-clinic Dosing ^l			x	x	x	x								

- a Vital signs include blood pressure, pulse, respiration rate and temperature.
- b Health Related Quality of Life surveys required for Early Discontinuation (ED) visit if not done within the last 24 weeks of the expected ED visit date.
- c Serum chemistry and Liver Function Tests: alkaline phosphatase, AST, ALT, GGT, total bilirubin, direct and indirect bilirubin, total protein, albumin, LDH, CPK, bicarbonate, BUN, calcium, chloride, creatinine, glucose, phosphorus, magnesium, potassium, sodium, uric acid, and amylase (reflex lipase testing is performed in subjects with total amylase > 1.5 × ULN), and PTH. PTH analyzed at all visits except for Screening. At Baseline, Weeks 24, 48, 72, and 96/ED, analyses of glucose will be done as part of the fasting metabolic assessments and not as part of the chemistry panel. Liver Function Tests: PT/INR will be done at Screening, Baseline, and Weeks 24, 48, and 96/ED and then as a reflex only test for ALT flares.
- d Fasting glucose and lipid panel (total cholesterol, HDL, direct LDL, triglycerides).
- e HBeAb and HBsAb reflex testing will be performed as needed.
- f An AFP > 50 ng/mL at Screening must have an appropriate evaluation (e.g., CT scan if not performed within the previous 6 months) in order to rule out HCC prior to being permitted to enter the study.
- g Urine sample collection for all subjects except only where available for subjects in Part A, Cohort 2 (ESRD subjects on HD).
- h The Baseline DXA can be performed at any time during the Screening period, but should be completed at least 14 days prior to the first dose of study drug to ensure an acceptable pre-dose DXA scan. The Week 24, Week 48, and Week 96 DXA window is –14 days only. DXA required for Early Discontinuation (ED) visit if not done within the last 12 weeks and should be done within ± 14 days of the expected ED visit date.

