- i Subjects must rest quietly in the supine position for a minimum of 5 minutes prior to the recording.
- j CPT [Appendix 7] assessment requires: total bilirubin, albumin, PT/INR, Ascites assessment, and Hepatic encephalopathy assessment. MELD assessment requires total bilirubin, serum creatinine, PT/INR, and serum sodium.
- k The visit window for the Week 24, Week 48, and Week 96 visits is –7 days only.
- l The Early Discontinuation (ED) visit should be performed within 72 hours of the last study drug dose (+ 3 days)

- m Subjects in Part A (renally impaired) who discontinue study drug due to HBsAg loss with confirmed seroconversion to anti-HBs on or after the Week 24 visit, will be followed off treatment every 4 weeks for 12 weeks and then per the original study visit schedule through Week 96/ED. Subjects in Part A (renally impaired) who have received at least one dose of study drug and permanently discontinue study drug for reasons other than HBsAg loss with confirmed seroconversion to anti-HBs will be followed every 4 weeks for 24 weeks off treatment or up to initiation of appropriate, alternative HBV therapy, whichever occurs first. Use of appropriate, alternative HBV therapy is strongly encouraged. For subjects in Part B (hepatic impairment) who permanently discontinue study drug, immediate initiation of appropriate, alternative HBV therapy is strongly recommended.
- n Any subject with a post baseline $eGFR_{CG} < 15$ mL/min must have serum creatinine measured again within 3 calendar days of receipt of results. At the time of this repeat serum creatinine assessment, serum Cystatin C will also be measured and the eGFR by CKD-EPI (cystatin C) will be calculated and compared with the baseline measurement. Any subjects who have an $eGFR_{CG} < 15$ mL/min that also experience $> 20\%$ reduction in eGFR by CKD-EPI (cystatin C) from baseline or who have other clinical and/or laboratory evidence of acute renal failure will be discussed with the Medical Monitor and may discontinue from study drugs.
- o Blood for selected bone biomarkers and urine for selected renal biomarkers will be collected in a fasted state. The fasting urine sample will be collected for all subjects except Part A, Cohort 2 (ESRD subjects on HD). Required for ED visit if the last sample was not collected within the last 12 weeks.

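### The 24-week look-back on the early-discontinuation HRQoL surveys leaves subjects who stop before the Week 24 visit with a Baseline survey only, and most who stop in Weeks 24 to 72 without a survey at exit (minor)

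*Protocol*

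**What the plan says.** The Synopsis (Study Procedures/Frequency) sets the schedule: "Health Related Quality of Life (HRQoL) Surveys (SF-36, CLDQ, WPAI, and EQ-5D-3L) at Baseline, Weeks 24, 48, and 96/ED". The HRQoL row of the Appendix 2 table matches it, with no survey at Weeks 4, 8, 12, 36, 60 or 72.

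The exit survey is conditional in three places, and they agree:

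- Synopsis: "The ED visit HRQoLs should be done if not done within the last 24 weeks of this visit".
- Section 6.5: the surveys "are done only if not done within the past 24 weeks of the ED visit". The word *only* makes this a restriction and not just the absence of a requirement.
- Appendix 2, footnote b: "Health Related Quality of Life surveys required for Early Discontinuation (ED) visit if not done within the last 24 weeks", counted from the expected date of the early discontinuation (ED) visit.

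Other assessments at the same visit are treated differently. In Section 6.5, FibroTest, CPT, MELD and the Health Utilization questions carry no look-back. DXA has a shorter one: "DXA required for Early Discontinuation (ED) visit if not done within the last 12 weeks". The bone and renal biomarkers and the fasting metabolic tests also use 12 weeks.

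**The concern.** Surveys fall 24 weeks apart up to Week 48, and the rule looks back 24 weeks. Up to Week 72, a subject who has kept to the schedule will nearly always have a survey inside the look-back. FibroTest, CPT and MELD follow the same Baseline, 24, 48 and 96 pattern but are collected at every ED visit.

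The sharpest case is an exit before the Week 24 visit. The survey that cancels the exit survey is then the Baseline one, completed before the first dose, so the subject has no on-treatment HRQoL.

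For most subjects later visits do not recover the data. The treatment-free follow-up assessments (Section 6.4.3) apply to Part A only and list no HRQoL, and the Follow Up column of the HRQoL row is blank. Section 6.5 asks sites to keep subjects in follow-up after dosing stops, but Section 6.4.2 defines that follow-up as those same visits. The exception is Part A subjects who stop after HBsAg seroconversion and later return to the original schedule (Section 6.4.1).

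If exits are related to worsening health, HRQoL summaries will under-represent the subjects who worsened. Under the default in Section 8.3, endpoints not named there are not imputed unless specified otherwise. A subject with no post-baseline survey would then contribute nothing to a summary of change. The study has no control arm against which to judge such a loss.

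**Working it through.** The plan gives no figure for how often the exit survey falls due and no expected discontinuation rate, so there is nothing to reproduce.

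**Inputs.** Surveys on days 0, 168, 336 and 672 (Baseline, Weeks 24, 48, 96; Synopsis and Appendix 2). Look-back 24 × 7 = 168 days. Window for the survey visits, Appendix 2 footnote k: "The visit window for the Week 24, Week 48, and Week 96 visits is –7 days only". ED timing, Section 6.5: "The ED Visit should be performed within 72 hours (i.e., visit window is + 3 days) of the last study drug dose", so exit and survey dates differ by at most 3 days.

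**Rule.** With the ED visit on day *t* and the last survey on day *s*, the survey is due if *t* − *s* > 168.

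**All scheduled surveys done on the nominal day**

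| ED day | Last survey | Largest *t* − *s* | Due? |
|---|---|---|---|
| 1–167 | 0 | 167 | No |
| 169–335 | 168 | 167 | No |
| 337–504 | 336 | 168 | No |
| 505–671 | 336 | 335 | Yes, from 505 − 336 = 169 |

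The survey first falls due on day 505, just after Week 72. It is due in (96 − 72)/96 = 24/96 = 25% of the treatment period.

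**Exceptions before Week 72**

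- Week 24 survey 7 days early (day 161) and Week 48 survey not yet done: due on days 330–335.
- Week 48 survey 7 days early (day 329): due from day 498 (Week 71.1).
- Week 24 survey missed: due on days 169–335.
- Week 48 survey missed: due from day 337.
- Both missed: due from day 169.

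No exception applies before Week 24.

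**Headcount.** Assume that 10–20% stop early, evenly over 96 weeks, with scheduled surveys done. The share stopping before Week 72 is 72/96 = 75%; before Week 24 it is 24/96 = 25%.

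| | Planned | Stop early | No exit survey (75%) | No post-baseline survey (25%) |
|---|---|---|---|---|
| All | 120 | 12–24 | 9–18 | 3–6 |
| Part A | 90 | 9–18 | 6.8–13.5 | 2.3–4.5 |
| Part B | 30 | 3–6 | 2.3–4.5 | 0.8–1.5 |

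The split matters because Section 8.2 provides no combined summary of Parts A and B. If exits cluster early, the last column rises.

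Two figures in the protocol give a crude check on the 10–20%. In the two Phase 3 studies, 63/1298 = 4.9% had stopped blinded drug by the Week 48 cutoff (Section 1.2.3); doubled for 96 weeks, that is 9.8%. In the decompensated-disease study, 69/112 completed 168 weeks of double-blind therapy (Section 1.2.4.3). The other 43/112 = 38.4%, some of whom switched to open-label drug, scale to 38.4% × 96/168 = 21.9%. Neither population matches this one.

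**With a 12-week look-back (84 days).** The survey is due on days 85–167, 253–335 and 421–671, or 12 + 12 + 36 = 60 of 96 weeks (62.5%). Exits before Week 12 still have Baseline only: 12/96 = 12.5% of 12–24, or 1.5–3 subjects.

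**The case against.** The strongest case against the point is that this is a consistent sponsor choice to avoid repeating four questionnaires, in a measure with no visible endpoint. HRQoL is not among the primary or secondary endpoints, the exploratory ones are redacted, and the study is exploratory and descriptive. Subjects leaving in Weeks 24–72 already have a post-baseline survey. Clinical worsening at exit is still recorded through adverse events, chemistry, eGFR, FibroTest, CPT, MELD and the Health Utilization questions. The headcount rests on an assumed discontinuation rate. All of this stands, and it is why the point is minor.

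It is also fair that removing the look-back does not by itself put the data to use. A survey at Week 6, say, enters a Week 24 summary only if a window or imputation rule places it there, and none is visible for HRQoL. The fix must cover this.

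Several stronger readings are tempting, but the documents do not support them:

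- *Nobody who leaves before Week 72 is surveyed at exit.* The −7 day windows and missed surveys create exceptions. For a missed Week 24 or Week 48 survey the rule works as a catch-up.
- *Every exit before Week 24 lacks on-treatment HRQoL.* The Week 24 visit can take place from Week 23 and includes the surveys unconditionally, so the loss concerns exits before that visit.
- *The surveys are lost for exactly the subjects who stop for toxicity or deterioration.* The rule depends on time since the last survey, not on the reason for stopping.
- *HRQoL results will be biased in favour of TAF.* The SAP document provided is an addendum that refers to a main SAP for windows and other rules. Without the HRQoL analysis, neither the size nor the direction of any bias can be shown.
- *Appendix 2 contradicts itself by marking ED in the HRQoL row.* That row carries footnote b, so the mark is expressly conditional.

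**Conclusion.** The point holds as a minor gap in data collection. It is not an inconsistency between passages. Followed exactly, the rule gives no exit survey through Week 72 to a subject whose scheduled surveys were done, except in the short gaps opened by the visit windows. It leaves anyone who stops before the Week 24 visit with a pre-treatment survey only.

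The schedule arithmetic needs no assumption beyond reading *within 24 weeks* as up to and including 168 days. The headcount of about 9–18 without an exit survey and 3–6 without any post-baseline survey assumes 10–20% early discontinuation, even exits over 96 weeks and scheduled surveys done. That HRQoL summaries would under-represent subjects who worsened is conditional on exits being related to health.

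**What to change.** **Collection.** In the Synopsis, Section 6.5 and Appendix 2 footnote b, delete the 24-week look-back and give SF-36, CLDQ, WPAI and EQ-5D-3L at every ED visit, as is already done for FibroTest, CPT and MELD. Where the ED visit coincides with a scheduled survey visit, one administration serves both. Adopting the 12-week look-back used for DXA is a weaker alternative, because exits before Week 12 would still have Baseline only.

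**Analysis.** Report, by Part, how many discontinuers have no exit survey and how many have no post-baseline survey. State how ED surveys are used, for example in a summary of change from Baseline to the last on-treatment survey alongside the by-visit summaries. Otherwise the added data may fall outside every analysis window.

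**Cost.** Wording in three places, and four questionnaires per early discontinuer at a visit that already takes place. Some will repeat a recent survey. The SAP addendum concerns the final analysis. If collection has closed, only the reporting step remains, and it needs no new data.

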Appendix 3. Management of Clinical and Laboratory Adverse Events

Appendix 4. GSI Grading Scale for Severity of Adverse Events and Laboratory Abnormalities

Antiviral Toxicity Grading Scale Version: 01 April 2015

HEMATOLOGY				
	Grade 1	Grade 2	Grade 3	Grade 4
Hemoglobin				
HIV POSITIVE	8.5 to 10.0 g/dL	7.5 to < 8.5 g/dL	6.5 to < 7.5 g/dL	< 6.5 g/dL
Adult and Pediatric ≥ 57 Days	85 to 100 g/L	75 to < 85 g/L	65 to < 75 g/L	< 65 g/L
HIV NEGATIVE	10.0 to 10.9 g/dL	9.0 to < 10.0 g/dL	7.0 to < 9.0 g/dL	< 7.0 g/dL
Adult and Pediatric ≥ 57 Days	100 to 109 g/L	90 to < 100 g/L	70 to < 90 g/L	< 70 g/L
	OR	OR	OR	
	Any decrease from Baseline	Any decrease from Baseline	Any decrease from Baseline	
	2.5 to < 3.5 g/dL	3.5 to < 4.5 g/dL	≥ 4.5 g/dL	
	25 to < 35 g/L	35 to < 45 g/L	≥ 45 g/L	
Infant, 36–56 Days (HIV POSITIVE OR NEGATIVE)	8.5 to 9.4 g/dL	7.0 to < 8.5 g/dL	6.0 to < 7.0 g/dL	< 6.0 g/dL
	85 to 94 g/L	70 to < 85 g/L	60 to < 70 g/L	< 60 g/L
Infant, 22–35 Days (HIV POSITIVE OR NEGATIVE)	9.5 to 10.5 g/dL	8.0 to < 9.5 g/dL	7.0 to < 8.0 g/dL	< 7.0 g/dL
	95 to 105 g/L	80 to < 95 g/L	70 to < 80 g/L	< 70 g/L
Infant, 1–21 Days (HIV POSITIVE OR NEGATIVE)	12.0 to 13.0 g/dL	10.0 to < 12.0 g/dL	9.0 to < 10.0 g/dL	< 9.0 g/dL
	120 to 130 g/L	100 to < 120 g/L	90 to < 100 g/L	< 90 g/L
Absolute Neutrophil Count (ANC)				
Adult and Pediatric, ≥ 7 Months[#]	1000 to 1300/mm ³	750 to < 1000/mm ³	500 to < 750/mm ³	< 500/mm ³
	1.00 to 1.30 GI/L	0.75 to < 1.00 GI/L	0.50 to < 0.75 GI/L	< 0.50 GI/L
Absolute CD4+ Count				
HIV NEGATIVE ONLY				
Adult and Pediatric > 13 Years	300 to 400/mm ³	200 to < 300/mm ³	100 to < 200/mm ³	< 100/mm ³
	300 to 400/μL	200 to < 300/μL	100 to < 200/μL	< 100/μL

HEMATOLOGY				
	Grade 1	Grade 2	Grade 3	Grade 4
Absolute Lymphocyte Count HIV NEGATIVE ONLY Adult and Pediatric > 13 Years	600 to 650/mm ³ 0.60 to 0.65 GI/L	500 to < 600/mm ³ 0.50 to < 0.60 GI/L	350 to < 500/mm ³ 0.35 to < 0.50 GI/L	< 350/mm ³ < 0.35 GI/L
Platelets	100,000 to < 125,000/mm ³ 100 to < 125 GI/L	50,000 to < 100,000/mm ³ 50 to < 100 GI/L	25,000 to < 50,000/mm ³ 25 to < 50 GI/L	< 25,000/mm ³ < 25 GI/L
WBCs	2000/mm ³ to 2500/mm ³ 2.00 GI/L to 2.50 GI/L	1,500 to < 2,000/mm ³ 1.50 to < 2.00 GI/L	1000 to < 1,500/mm ³ 1.00 to < 1.50 GI/L	< 1000/mm ³ < 1.00 GI/L
Hypofibrinogenemia	100 to 200 mg/dL 1.00 to 2.00 g/L	75 to < 100 mg/dL 0.75 to < 1.00 g/L	50 to < 75 mg/dL 0.50 to < 0.75 g/L	< 50 mg/dL < 0.50 g/L
Hyperfibrinogenemia	> ULN to 600 mg/dL > ULN to 6.0 g/L	> 600 mg/dL > 6.0 g/L	— —	— —
Fibrin Split Product	20 to 40 µg/mL 20 to 40 mg/L	> 40 to 50 µg/mL > 40 to 50 mg/L	> 50 to 60 µg/mL > 50 to 60 mg/L	> 60 µg/mL > 60 mg/L
Prothrombin Time (PT)	> 1.00 to 1.25 × ULN	> 1.25 to 1.50 × ULN	> 1.50 to 3.00 × ULN	> 3.00 × ULN
International Normalized Ratio of prothrombin time (INR)	1.1 to 1.5 x ULN	>1.5 to 2.0 x ULN	>2.0 to 3.0 x ULN	>3.0 x ULN
Activated Partial Thromboplastin Time (APTT)	> 1.00 to 1.66 × ULN	> 1.66 to 2.33 × ULN	> 2.33 to 3.00 × ULN	> 3.00 × ULN
Methemoglobin	5.0 to 10.0%	> 10.0 to 15.0%	> 15.0 to 20.0%	> 20.0%

An overlap between the Grade 1 scale and the Lab's normal range for absolute neutrophils may result for pediatric subjects. Please follow the Gilead convention of grading any result within the LLN and ULN a 0.

CHEMISTRY				
	Grade 1	Grade 2	Grade 3	Grade 4
Hyponatremia	130 to <LLN mEq/L 130 to <LLN mmol/L	125 to < 130 mEq/L 125 to < 130 mmol/L	121 to < 125 mEq/L 121 to < 125 mmol/L	< 121 mEq/L < 121 mmol/L
Hypernatremia	>ULN to 150 mEq/L >ULN to 150 mmol/L	> 150 to 154 mEq/L > 150 to 154 mmol/L	> 154 to 159 mEq/L > 154 to 159 mmol/L	> 159 mEq/L > 159 mmol/L
Hypokalemia Adult and Pediatric ≥ 1 Year	3.0 to <LLN mEq/L 3.0 to <LLN mmol/L	2.5 to < 3.0 mEq/L 2.5 to < 3.0 mmol/L	2.0 to < 2.5 mEq/L 2.0 to < 2.5 mmol/L	< 2.0 mEq/L < 2.0 mmol/L
Infant <1 Year	3.0 to 3.4 mEq/L 3.0 to 3.4 mmol/L	2.5 to < 3.0 mEq/L 2.5 to <3.0 mmol/L	2.0 to < 2.5 mEq/L 2.0 to <2.5 mmol/L	< 2.0 mEq/L <2.0 mmol/L
Hyperkalemia Adult and Pediatric ≥ 1 Year	5.6 to 6.0 mEq/L 5.6 to 6.0 mmol/L	> 6.0 to 6.5 mEq/L > 6.0 to 6.5 mmol/L	> 6.5 to 7.0 mEq/L > 6.5 to 7.0 mmol/L	> 7.0 mEq/L > 7.0 mmol/L
Infant <1 Year	>ULN to 6.0 mEq/L >ULN to 6.0 mmol/L	> 6.0 to 6.5 mEq/L > 6.0 to 6.5 mmol/L	> 6.5 to 7.0 mEq/L > 6.5 to 7.0 mmol/L	> 7.0 mEq/L > 7.0 mmol/L
Hypoglycemia Adult and Pediatric ≥ 1 Month	55 to 64 mg/dL 3.03 to 3.58 mmol/L	40 to < 55 mg/dL 2.20 to < 3.03 mmol/L	30 to < 40 mg/dL 1.64 to < 2.20 mmol/L	< 30 mg/dL < 1.64 mmol/L
Infant, < 1 Month	50 to 54 mg/dL 2.8 to 3.0 mmol/L	40 to < 50 mg/dL 2.2 to < 2.8 mmol/L	30 to < 40 mg/dL 1.7 to < 2.2 mmol/L	< 30 mg/dL < 1.7 mmol/L
Hyperglycemia, Nonfasting	116 to 160 mg/dL 6.42 to 8.91 mmol/L	> 160 to 250 mg/dL > 8.91 to 13.90 mmol/L	> 250 to 500 mg/dL > 13.90 to 27.79 mmol/L	> 500 mg/dL > 27.79 mmol/L
Hyperglycemia, Fasting	110 to 125 mg/dL 6.08 to 6.96 mmol/L	>125 to 250 mg/dL >6.96 to 13.90 mmol/L	>250 to 500 mg/dL >13.90 to 27.79 mmol/L	>500 mg/dL >27.79 mmol/L

CHEMISTRY				
	Grade 1	Grade 2	Grade 3	Grade 4
Hypocalcemia (corrected for albumin if appropriate*) Adult and Pediatric ≥2 Years	7.8 <LLN mg/dL 1.94 to <LLN mmol/L	7.0 to <7.8 mg/dL 1.74 to <1.94 mmol/L	6.1 to <7.0 mg/dL 1.51 to <1.74 mmol/L	<6.1 mg/dL <1.51 mmol/L
Pediatric ≥7 days -2 Years	7.8 to 8.4 mg/dL 1.94 to 2.10 mmol/L	7.0 to <7.8 mg/dL 1.74 to <1.94 mmol/L	6.1 to <7.0 mg/dL 1.51 to <1.74 mmol/L	<6.1 mg/dL <1.51 mmol/L
Infant, < 7 Days	6.5 to 7.5 mg/dL 1.61 to 1.88 mmol/L	6.0 to <6.5 mg/dL 1.49 to <1.61 mmol/L	5.5 to <6.0 mg/dL 1.36 to <1.49 mmol/L	<5.5 mg/dL <1.36 mmol/L
Hypercalcemia (corrected for albumin if appropriate*) Adult and Pediatric ≥ 7 Days	>ULN to 11.5 mg/dL >ULN to 2.88 mmol/L	>11.5 to 12.5 mg/dL >2.88 to 3.13 mmol/L	>12.5 to 13.5 mg/dL >3.13 to 3.38 mmol/L	>13.5 mg/dL >3.38 mmol/L
Infant, < 7 Days	11.5 to 12.4 mg/dL 2.86 to 3.10 mmol/L	>12.4 to 12.9 mg/dL >3.10 to 3.23 mmol/L	>12.9 to 13.5 mg/dL >3.23 to 3.38 mmol/L	>13.5 mg/dL >3.38 mmol/L
Hypocalcemia (ionized)	3.0 mg/dL to <LLN 0.74 mmol/L to <LLN	2.5 to <3.0 mg/dL 0.62 to <0.74 mmol/L	2.0 to <2.5 mg/dL 0.49 to <0.62 mmol/L	<2.0 mg/dL <0.49 mmol/L
Hypercalcemia (ionized)	>ULN to 6.0 mg/dL >ULN to 1.50 mmol/L	>6.0 to 6.5 mg/dL >1.50 to 1.63 mmol/L	>6.5 to 7.0 mg/dL >1.63 to 1.75 mmol/L	>7.0 mg/dL >1.75 mmol/L
Hypomagnesemia	1.40 to <LLN mg/dL 1.2 to <LLN mEq/L 0.58 to <LLN mmol/L	1.04 to <1.40 mg/dL 0.9 to <1.2 mEq/L 0.43 to <0.58 mmol/L	0.67 to <1.04 mg/dL 0.6 to <0.9 mEq/L 0.28 to <0.43 mmol/L	<0.67 mg/dL <0.6 mEq/L <0.28 mmol/L

CHEMISTRY				
	Grade 1	Grade 2	Grade 3	Grade 4
Hypophosphatemia Adult and Pediatric > 14 Years	2.0 to < LLN mg/dL 0.63 to < LLN mmol/L	1.5 to < 2.0 mg/dL 0.47 to < 0.63 mmol/L	1.0 to < 1.5 mg/dL 0.31 to < 0.47 mmol/L	< 1.0 mg/dL < 0.31 mmol/L
Pediatric 1 Year–14 Years	3.0 to <LLN mg/dL 0.96 to <LLN mmol/L	2.5 to < 3.0 mg/dL 0.80 to < 0.96 mmol/L	1.5 to < 2.5 mg/dL 0.47 to < 0.80 mmol/L	< 1.5 mg/dL < 0.47 mmol/L
Pediatric < 1 Year	3.5 to <LLN mg/dL 1.12 to <LLN mmol/L	2.5 to < 3.5 mg/dL 0.80 to < 1.12 mmol/L	1.5 to < 2.5 mg/dL 0.47 to < 0.80 mmol/L	< 1.5 mg/dL < 0.47 mmol/L
Hyperbilirubinemia Adult and Pediatric > 14 Days	> 1.0 to 1.5 × ULN	> 1.5 to 2.5 × ULN	> 2.5 to 5.0 × ULN	> 5.0 × ULN
Infant, ≤ 14 Days (non-hemolytic)	NA	20.0 to 25.0 mg/dL 342 to 428 μmol/L	> 25.0 to 30.0 mg/dL > 428 to 513 μmol/L	> 30.0 mg/dL > 513 μmol/L
Infant, ≤ 14 Days (hemolytic)	NA	NA	20.0 to 25.0 mg/dL 342 to 428 μmol/L	> 25.0 mg/dL > 428 μmol/L
Blood Urea Nitrogen	1.25 to 2.50 × ULN	> 2.50 to 5.00 × ULN	> 5.00 to 10.00 × ULN	> 10.00 × ULN
Hyperuricemia	>ULN to 10.0 mg/dL >ULN to 597 μmol/L	> 10.0 to 12.0 mg/dL > 597 to 716 μmol/L	> 12.0 to 15.0 mg/dL > 716 to 895 μmol/L	> 15.0 mg/dL > 895 μmol/L
Hypouricemia Adult and Pediatric ≥ 1 year	1.5 mg/dL to < LLN 87 μmol/L to < LLN N/A	1.0 to < 1.5 mg/dL 57 to < 87 μmol/L 1.0 mg/dl to <LLN- 57 μmol to <LLN	0.5 to < 1.0 mg/dL 27 to < 57 μmol/L 0.5 to < 1.0 mg/dL 27 to < 57 μmol/L	< 0.5 mg/dL < 27 μmol/L < 0.5 mg/dL < 27 μmol/L
Infant < 1 Year				

CHEMISTRY				
	Grade 1	Grade 2	Grade 3	Grade 4
Creatinine**	> 1.50 to 2.00 mg/dL > 133 to 177 µmol/L	> 2.00 to 3.00 mg/dL > 177 to 265 µmol/L	> 3.00 to 6.00 mg/dL > 265 to 530 µmol/L	> 6.00 mg/dL > 530 µmol/L
Bicarbonate Adult and Pediatric ≥ 4 Years	16.0 mEq/L to < LLN 16.0 mmol/L to < LLN	11.0 to < 16.0 mEq/L 11.0 to < 16.0 mmol/L	8.0 to < 11.0 mEq/L 8.0 to < 11.0 mmol/L	< 8.0 mEq/L < 8.0 mmol/L
Pediatric < 4 Years	NA	11.0 mEq/L to <LLN 11.0 mmol/L to <LLN	8.0 to < 11.0 mEq/L 8.0 to < 11.0 mmol/L	< 8.0 mEq/L < 8.0 mmol/L
Triglycerides (Fasting)	NA	500 to 750 mg/dL 5.64–8.47 mmol/L	> 750 to 1200 mg/dL > 8.47–13.55 mmol/L	> 1200 mg/dL > 13.55 mmol/L
LDL (Fasting) Adult	130 to 160 mg/dL 3.35 to 4.15 mmol/L	>160 to 190 mg/dL >4.15 to 4.92 mmol/L	> 190 mg/dL >4.92 mmol/L	NA
LDL (Fasting) Pediatric >2 to <18 years	110 to 130 mg/dL 2.84 to 3.37 mmol/L	>130 to 190 mg/dL >3.37 to 4.92 mmol/L	> 190 mg/dL >4.92 mmol/L	NA
Hypercholesterolemia (Fasting)	200 to 239 mg/dL 5.16 to 6.19 mmol/L	> 239 to 300 mg/dL > 6.19 to 7.77 mmol/L	> 300 mg/dL > 7.77 mmol/L	NA
Pediatric < 18 Years	170 to 199 mg/dL 4.39 to 5.15 mmol/L	> 199 to 300 mg/dL > 5.15 to 7.77 mmol/L	> 300 mg/dL > 7.77 mmol/L	NA
Creatine Kinase	3.0 to < 6.0 × ULN	6.0 to < 10.0 × ULN	10.0 to < 20.0 × ULN	≥ 20.0 × ULN

* Calcium should be corrected for albumin if albumin is < 4.0 g/dL

** An overlap between the Grade 1 scale and the Lab's normal range for creatinine may result for Male subjects >70 yrs. Please follow the Gilead convention of grading any result within the LLN and ULN a 0.

ENZYMES				
	Grade 1	Grade 2	Grade 3	Grade 4
AST (SGOT)	1.25 to 2.50 × ULN	> 2.50 to 5.00 × ULN	> 5.00 to 10.00 × ULN	> 10.00 × ULN
ALT (SGPT)	1.25 to 2.50 × ULN	> 2.50 to 5.00 × ULN	> 5.00 to 10.00 × ULN	> 10.00 × ULN
GGT	1.25 to 2.50 × ULN	> 2.50 to 5.00 × ULN	> 5.00 to 10.00 × ULN	> 10.00 × ULN
Alkaline Phosphatase	1.25 to 2.50 × ULN	> 2.50 to 5.00 × ULN	> 5.00 to 10.00 × ULN	> 10.00 × ULN
Total Amylase	> 1.0 to 1.5 × ULN	> 1.5 to 2.0 × ULN	> 2.0 to 5.0 × ULN	> 5.0 × ULN
Pancreatic Amylase	> 1.0 to 1.5 × ULN	> 1.5 to 2.0 × ULN	> 2.0 to 5.0 × ULN	> 5.0 × ULN
Lipase	> 1.0 to 1.5 × ULN	> 1.5 to 3.0 × ULN	> 3.0 to 5.0 × ULN	> 5.0 × ULN
Albumin	-	2.0 to < LLN g/dL	< 2.0 g/dL	NA
Pediatrics <16 years		20 to < LLN g/L	< 20 g/L	
≥ 16 years	3.0 g/dL to < LLN 30 g/L to < LLN	2.0 to < 3.0 g/dL 20 to < 30 g/L	< 2.0 g/dL < 20 g/L	NA

URINALYSIS				
	Grade 1	Grade 2	Grade 3	Grade 4
Hematuria (Dipstick)	1+	2+	3-4+	NA
Hematuria (Quantitative) See Note below				
Females	>ULN - 10 RBC/HPF	> 10-75 RBC/HPF	> 75 RBC/HPF	NA
Males	6-10 RBC/HPF	> 10-75 RBC/HPF	> 75 RBC/HPF	NA
Proteinuria (Dipstick)	1+	2-3+	4+	NA
Proteinuria, 24 Hour Collection				
Adult and Pediatric ≥ 10 Years	200 to 999 mg/24 h	>999 to 1999 mg/24 h	>1999 to 3500 mg/24 h	> 3500 mg/24 h
Pediatric > 3 Mo to < 10 Years	201 to 499 mg/m ² /24 h	>499 to 799 mg/m ² /24 h	>799 to 1000 mg/m ² /24 h	> 1000 mg/ m ² /24 h
Glycosuria (Dipstick)	1+	2-3+	4+	NA

Notes:

- Toxicity grades for Quantitative and Dipstick Hematuria will be assigned by Covance Laboratory, however for other laboratories, toxicity grades will only be assigned to Dipstick Hematuria.
- With the exception of lipid tests, any graded laboratory test with a result that is between the LLN and ULN should be assigned Grade 0.
- If the severity of a clinical AE could fall under either one of two grades (e.g., the severity of an AE could be either Grade 2 or Grade 3), select the higher of the two grades for the AE.

CARDIOVASCULAR				
	Grade 1	Grade 2	Grade 3	Grade 4
Cardiac Arrhythmia (general) (By ECG or physical exam)	Asymptomatic AND No intervention indicated	Asymptomatic AND Non-urgent medical intervention indicated	Symptomatic, non-life-threatening AND Non-urgent medical intervention indicated	Life-threatening arrhythmia OR Urgent intervention indicated
Cardiac-ischemia/Infarction	NA	NA	Symptomatic ischemia (stable angina) OR Testing consistent with ischemia	Unstable angina OR Acute myocardial infarction
Hemorrhage (significant acute blood loss)	NA	Symptomatic AND No transfusion indicated	Symptomatic AND Transfusion of ≤ 2 units packed RBCs (for children ≤ 10 cc/kg) indicated	Life-threatening hypotension OR Transfusion of > 2 units packed RBCs indicated (for children ≤ 10 cc/kg) indicated
Hypertension (with repeat testing at same visit)	140–159 mmHg systolic OR 90–99 mmHg diastolic	> 159–179 mmHg systolic OR > 99–109 mmHg diastolic	> 179 mmHg systolic OR > 109 mmHg diastolic	Life-threatening consequences (eg, malignant hypertension) OR Hospitalization (other than ER visit) indicated
Pediatric ≤ 17 Years (with repeat testing at same visit)	NA	91st–94th percentile adjusted for age, height, and gender (systolic and/or diastolic)	≥ 95th percentile adjusted for age, height, and gender (systolic and/or diastolic)	Life-threatening consequences (eg, malignant hypertension) OR Hospitalization indicated (other than emergency room visit)
Hypotension	NA	Symptomatic, corrected with oral fluid replacement	Symptomatic, IV fluids indicated	Shock requiring use of vasopressors or mechanical assistance to maintain blood pressure
Pericardial Effusion	Asymptomatic, small effusion requiring no intervention	Asymptomatic, moderate or larger effusion requiring no intervention	Effusion with non-life-threatening physiologic consequences OR Effusion with nonurgent intervention indicated	Life-threatening consequences (eg, tamponade) OR Urgent intervention indicated

CARDIOVASCULAR				
	Grade 1	Grade 2	Grade 3	Grade 4
Prolonged PR Interval	PR interval 0.21 to 0.25 sec	PR interval > 0.25 sec	Type II 2nd degree AV block OR Ventricular pause > 3.0 sec	Complete AV block
Pediatric ≤ 16 Years	1st degree AV block (PR > normal for age and rate)	Type I 2nd degree AV block	Type II 2nd degree AV block	Complete AV block
Prolonged QTc	Asymptomatic, QTc interval 0.45 to 0.47 sec OR Increase interval < 0.03 sec above baseline	Asymptomatic, QTc interval 0.48 to 0.49 sec OR Increase in interval 0.03 to 0.05 sec above baseline	Asymptomatic, QTc interval ≥ 0.50 sec OR Increase in interval ≥ 0.06 sec above baseline	Life-threatening consequences, eg, Torsade de pointes or other associated serious ventricular dysrhythmia
Pediatric ≤ 16 Years	Asymptomatic, QTc interval 0.450 to 0.464 sec	Asymptomatic, QTc interval 0.465 to 0.479 sec	Asymptomatic, QTc interval ≥ 0.480 sec	Life-threatening consequences, eg, Torsade de pointes or other associated serious ventricular dysrhythmia
Thrombosis/Embolism	NA	Deep vein thrombosis AND No intervention indicated (eg, anticoagulation, lysis filter, invasive procedure)	Deep vein thrombosis AND Intervention indicated (eg, anticoagulation, lysis filter, invasive procedure)	Embolic event (eg, pulmonary embolism, life-threatening thrombus)
Vasovagal Episode (associated with a procedure of any kind)	Present without loss of consciousness	Present with transient loss of consciousness	NA	NA
Ventricular Dysfunction (congestive heart failure, CHF)	NA	Asymptomatic diagnostic finding AND intervention indicated	New onset with symptoms OR Worsening symptomatic CHF	Life-threatening CHF

RESPIRATORY				
	Grade 1	Grade 2	Grade 3	Grade 4
Bronchospasm (acute)	FEV1 or peak flow reduced to 70% to 80%	FEV1 or peak flow 50% to 69%	FEV1 or peak flow 25% to 49%	Cyanosis OR FEV1 or peak flow < 25% OR Intubation
Dyspnea or Respiratory Distress	Dyspnea on exertion with no or minimal interference with usual social & functional activities	Dyspnea on exertion causing greater than minimal interference with usual social & functional activities	Dyspnea at rest causing inability to perform usual social & functional activities	Respiratory failure with ventilatory support indicated
Pediatric < 14 Years	Wheezing OR minimal increase in respiratory rate for age	Nasal flaring OR Intercostal retractions OR Pulse oximetry 90% to 95%	Dyspnea at rest causing inability to perform usual social & functional activities OR Pulse oximetry < 90%	Respiratory failure with ventilatory support indicated

OCULAR/VISUAL				
	Grade 1	Grade 2	Grade 3	Grade 4
Uveitis	Asymptomatic but detectable on exam	Symptomatic anterior uveitis OR Medical intervention indicated	Posterior or pan-uveitis OR Operative intervention indicated	Disabling visual loss in affected eye(s)
Visual Changes (from baseline)	Visual changes causing no or minimal interference with usual social & functional activities	Visual changes causing greater than minimal interference with usual social & functional activities	Visual changes causing inability to perform usual social & functional activities	Disabling visual loss in affected eye(s)

SKIN				
	Grade 1	Grade 2	Grade 3	Grade 4
Alopecia	Thinning detectable by study participant or caregiver (for disabled adults)	Thinning or patchy hair loss detectable by health care provider	Complete hair loss	NA
